### **5.3 Strategies for Recruitment and Retention**

Sufficient subjects will be screened to allow for approximately 42 eligible subjects to be randomized at 2 US-based investigational sites.

Subjects will be mainly recruited via referrals. If radio, local print advertising, or any recruitment material is considered, prior Sponsor and IRB approval will be obtained. Potential subjects will be contacted via telephone for a preliminary screen of some of the inclusion and exclusion criteria. Only subjects who are able to provide voluntary informed consent will be admitted. Preliminarily eligible subjects will be invited to the clinic for complete screening, as set forth in the Schedule of Study Procedures.

### **5.4 Participant Withdrawal or Termination**

#### **5.4.1 Reasons for Withdrawal or Termination**

Participants are free to withdraw from participation in the study at any time upon request for any reason without prejudice to his or her future medical care by the physician or at the institution. A subject may be terminated from the study for any of the following reasons:

- Withdrawal of informed consent.
- Entry into the study in violation of the protocol.
- Any AE, laboratory abnormality, or other medical condition or situation occurs such that the study doctor or study staff believes continued participation in the study would not be in the best interest of the participant.

- The participant meets an exclusion criterion (either newly developed or not previously recognized) that precludes further study participation.
- Noncompliance with the protocol.
- At the discretion of the Investigator or Sponsor for any reason.

#### **5.4.2 Handling of Participant Withdrawals or Termination**

If a subject discontinues from the study prematurely, all efforts will be made to conduct early termination (ET) evaluations as thoroughly as possible up to the date of withdrawal at the time of discontinuation.

Subjects who discontinue from the study may be replaced unless it is due to one of the toxicity criteria in [Table 3](#), in which situation subjects will not be replaced.

#### **5.5 Premature Termination or Suspension of Study**

This study may be temporarily suspended or prematurely terminated if there is sufficient reasonable cause. Written notification, documenting the reason for study suspension or termination, will be provided by the suspending or terminating party to Bonti. If the study is prematurely terminated or suspended, the PI will promptly inform the IRB and will provide the reason(s) for the termination or suspension.

Circumstances that may warrant termination or suspension include, but are not limited to:

- Determination of unexpected, significant, or unacceptable risk to participants.
- Demonstration of efficacy that would warrant stopping.
- Insufficient compliance to protocol requirements.
- Data that are not sufficiently complete and/or evaluable.
- Determination of futility.

Study may resume once concerns about safety, protocol compliance, and/or data quality are addressed and satisfy the Sponsor, IRB and/or FDA.

## 6 STUDY AGENT

[REDACTED]

### **6.1.5 Dosing and Administration**

See [Section 4.1](#).

### **6.1.6 Route of Administration**

Intramuscular

### **6.1.7 Starting Dose and Dose Escalation Schedule**

See [Section 4.1](#).

### **6.1.8 Dose Adjustments/Modification/Delays**

If an intolerable dose is identified, a lower dose may be evaluated. This lower dose may be a repeat of the prior lower dose cohort or an intermediary dose between the intolerable dose and prior lower dose cohort.

Any dose cohort below the intolerable dose cohort may be repeated, if requested by the DRT, to better evaluate any finding at that dose level.

All dose escalation/adjustments or additional cohorts will be determined by the DRT up to a total of 9 dose cohorts for up to a total of 54 subjects.

### **6.1.9 Duration of Treatment**

Expected duration is approximately 6 weeks for each subject from the day of study treatment to the follow-up visit, and approximately 10 weeks from signing ICF to the follow-up exit.

The entire study duration is expected to take approximately seven months from the first visit of the first subject (screening) to the last visit of the last subject.

### **6.1.10 Tracking of Study Kit and Dose**

The Investigator will keep a record of the dates study drug kits received, the dose dispensed to each study subject from each kit. After dose is administered to the subject, the dispenser will collect and place the remaining vials back to the kit, and reseal it until CRA conducts final drug accountability which will be verified and reconciled on the Study Drug Kit Log and Study Drug Preparation Sheet. By the end of the study, the CRA upon conducting final drug accountability will instruct the dispenser or designee to ship any remaining study vials to the distribution center to be destroyed.

### **6.1.11 Replacement Procedures for Investigational Medicinal Product**

Instructions for resupply shipments or replacement of study drug are referenced in the study manual(s).

## **6.2 Investigational Product Accountability Procedures**

It is the responsibility of the Investigator to supervise accurate monitoring of the receipt, storage, dose preparation, and accounting of all study drug according to accepted medical and pharmaceutical practice. Copies of all invoices of study drug shipments must be retained. Accurate, original site records of study drug inventory and dispensing must be maintained using the forms provided study manual(s).

All study drug documentation must be maintained by the unblinded pharmacist or designated unblinded personnel. All disposition records must be made available for inspection by Sponsor or CRO upon request.

A Study Drug Kit Log will be provided for the accounting of study drug. Study Drug Kit Log forms will be provided for the accounting of study drug for each study subject and for maintaining the overall balance of vials. A reason(s) must be given for any amounts that are not accounted for.

Each site must keep all remaining study drug in the original vials until they are returned to the distribution center.

## 7 STUDY PROCEDURES AND SCHEDULE

### 7.1 Study Procedures/Evaluations

The principal Investigator and Sponsor must agree upon the format and content of the ICF before it is submitted to the IRB for approval. Written informed consent must be obtained from each subject prior to any study-related activities being conducted. The Investigator must retain all original signed and personally dated ICFs (together with any subsequent IRB-approved amended versions) in the subject's file. A copy of the original signed and dated ICF (and any amendments) must be given to the subject.

Subjects will be informed of findings (including AEs) from earlier cohorts if it is considered these could potentially affect the subject's willingness to participate or continue in the study. Depending on the nature, severity, and seriousness of these AEs, the ICF may be amended.

#### 7.1.1 Study Specific Procedures

- Informed Consent
- Demographics
- Assessment of inclusion/exclusion criteria
- Medical history
- Assessment of adverse event
- Height and weight
- Complete physical and focused neurological examinations
- Mini Physical and focused neurological examinations
- Prior and concomitant medications
- 12-lead ECG
- Body temperature, respiration rate, blood pressure, and pulse rate
- Serum chemistry, Lipids, Hematology
- Urinalysis
- Immunogenicity sample collection
- Screens for HIV and hepatitis B and C
- Screens for alcohol / drugs of abuse
- Serum/urine pregnancy test
- Study drug administration
- Standardized Facial Photography
- Facial Wrinkle Scale – Subject Assessment
- Facial Wrinkle Scale – Investigator Assessment

### **7.1.1.1 Informed Consent**

At the Screening Visit, prior to any procedures are performed, the site staff will obtain the signed ICF from each participant.

### **7.1.1.2 Demographics**

At the Screening Visit, the site staff will be responsible for collecting the age, sex, ethnicity, and race.

### **7.1.1.3 Assessment of Inclusion/Exclusion Criteria**

At the Screening and the Baseline (prior to dosing) Visits, the site staff will be responsible for reviewing the inclusion and exclusion criteria to determine the subject's eligibility for the study.

### **7.1.1.4 Medical History**

At the Screening Visit, medical history of the subject will be conducted. Any untoward medical occurrence that occurs after signing ICF is considered AE.

### **7.1.1.5 Assessment of Adverse Event**

Adverse events will be recorded beginning after signing the ICF until completion of the study until the final follow-up visit (Day 42), and will be evaluated by the Investigator for severity (using CTCAE version 4.03 criteria ([CTCAE 2010](#))), seriousness, and attributability to study medication. Further details on AEs, including definitions, elicitation, and reporting are provided in [Section 8](#).

### **7.1.1.6 Height and Weight**

At the Screening Visit, subject height will be recorded. Height (cm) measured from the Screen Visit will be carried forward to Day 0. At the Screening and Baseline (prior to dosing) Visits, subject weight (kg, in indoor clothing, but without shoes) will be measured.

### **7.1.1.7 Complete Physical and Focused Neurological Examinations**

At the Screening and the Baseline (prior to dosing) Visits, complete physical examinations (including but not limited to: dermatologic, head, eye, ear, nose, throat (HEENT), respiratory, cardiovascular, abdomen, lymph nodes, musculoskeletal) will be performed. Focused neurological examination will assess potential SOT per instructions in the [Appendix 1](#).

### **7.1.1.8 Mini Physical and Focused Neurological Examinations**

At Days 1, 2, 7, 14, 30 (EOS/ET), and 42 Visits, mini physical examination that is symptom-oriented will be performed. Focused neurological examination will assess potential SOT per instructions in the [Appendix 1](#).

### **7.1.1.9 Prior and Concomitant Medications**

At the Screening Visit, the Baseline Visit, and at all subsequent scheduled and unscheduled clinic visits, prior and concomitant medications will be assessed.

Medications taken within 30 days prior to the screening visit and up to the study drug administration will be considered to be prior medications. Concomitant medication is defined as any medication that is taken after the study drug administration (Day 0). Any use of prior and concomitant medications will be recorded on the Concomitant Medications electronic Case Report Form (eCRF). During the study, initiation of or change in concomitant medications to treat an AE must also be recorded on an AE eCRF for that AE.

### **7.1.1.10 12-Lead ECG**

At the Screening Visit, Day 2 Visit, and Day 30 (EOS/ET) Visit, a standard 12-lead ECG will be recorded in the supine position after at least 5 minutes rest. All ECG measures will be performed in triplicate, with each consecutive measure approximately 1 minute apart. In addition, where applicable, ECGs will be performed prior to blood draws.

The definitive ECG assessments will be conducted by a central ECG-reading facility. The assessment of the ECG by the central ECG-reading facility will include heart rate (HR), ECG intervals/durations (RR interval, PR interval, QRS duration, QT interval, and QTc interval using Fridericia's and Bazett's corrections [QTcF and QTcB intervals, respectively; see [List of Abbreviations and Glossary of Terms](#)), and assessments of the waveform. The tracings may be reviewed and reported both locally and by a blinded central reader. In the event that the clinical study site and the central reader disagree on the interpretation of the results, the central reader's interpretation will be considered final. The centrally reported ECG results will be used in the data analyses.

### **7.1.1.11 Body Temperature, Respiration Rate, Blood Pressure, and Pulse Rate**

At the Screening Visit, Baseline Visit (Day 0), and at all subsequent scheduled clinic visits till Day 30 (EOS/ET) visit, vital signs including body temperature, respiration rate, blood pressure, and pulse rate will be recorded. In addition, where applicable, vital sign data will be collected prior to blood draws.

Body temperature taken either orally or aurally will be the same throughout the study. Respiration rate will be taken at a quiet resting state prior to blood pressure (BP) and pulse rate measurements. Supine blood pressure (BP; systolic and diastolic) and pulse rate will be evaluated after at least 5 minutes rest.

#### **7.1.1.12 Serum Chemistry, Lipids, Hematology**

At the Screening Visit, Day 7 Visit, and Day 30 (EOS/ET) Visit, samples for routine serum chemistry, lipids, and hematology will be collected (see [Appendix 3](#) for specific tests). Fasting for serum chemistry and lipids will begin at midnight until testing.

The samples will be analyzed by a central laboratory (with the appropriate accreditations or certifications). If clinically indicated, tests may be taken at additional times. Any clinical laboratory findings considered to be clinically significant changes from screening will be recorded as an AE on the eCRF (unless the laboratory finding is a feature of a specific diagnosis, when only the diagnosis will be recorded). Any clinically significant abnormal values that persist will be followed until they have been resolved or the Investigator, in consultation with the Medical Monitor or designee, assesses them to be chronic or stable.

#### **7.1.1.13 Urinalysis**

At the Screening Visit, Day 7 Visit, and Day 30 (EOS/ET) Visit, urine samples for urinalysis will be collected (see [Appendix 3](#) for specific tests).

The samples will be analyzed by a central laboratory (with the appropriate accreditations or certifications). If clinically indicated, tests may be taken at additional times. Any clinical laboratory findings considered to be clinically significant changes from screening will be recorded as an AE on the eCRF (unless the laboratory finding is a feature of a specific diagnosis, when only the diagnosis will be recorded). Any clinically significant abnormal values that persist will be followed until they have been resolved or the Investigator, in consultation with the Medical Monitor or designee, assesses them to be chronic or stable.

#### **7.1.1.14 Immunogenicity Sample Collection**

[REDACTED]

#### **7.1.1.15 Screens for HIV and Hepatitis B and C**

At the Screening Visit only, blood samples for testing HIV antibody, hepatitis B surface antigen, and hepatitis C antibody will be collected.

The samples will be analyzed by a central laboratory (with the appropriate accreditations or certifications). Any positive findings at the Screening will exclude subject from participating in the study.

#### **7.1.1.16 Screens for Alcohol / Drugs of Abuse**

At the Screening Visit, Baseline (prior to dosing) Visit, Day 7 Visit, and Day 30 (EOS/ET) Visit, urine samples for screening drugs of abuse and saliva samples for screening alcohol will be collected and performed (see [Appendix 3](#) for specific tests).

The samples will be analyzed at the study site. Any positive findings at the Screening or Baseline Visit will exclude subject from participating in the study.

#### **7.1.1.17 Pregnancy Test**

At the Screening Visit, blood samples for pregnancy test for women of child bearing potential will be collected. The samples will be analyzed by a central laboratory (with the appropriate accreditations or certifications).

At the Baseline (prior to dosing) Visit and Day 30 (EOS/ET) Visit, urine samples for pregnancy test for women of child bearing potential will be collected. The samples will be analyzed at the study site. Any positive findings at the Screening or Baseline Visit will exclude subject from participating in the study. See [Section 8.5.2](#) in the event of any positive findings during the study.

#### **7.1.1.18 Study Drug Administration**

At the Baseline Visit, upon conducting all specified pre-dose assessment and confirming subjects remain eligible for the study, study drug will be administered. Six subjects in a cohort will be treated with either EB-001 or placebo in a ratio of 5:1 in a double-blind manner.

#### **7.1.1.19 Standardized Facial Photography**

At the Baseline (prior to dosing) Visit, and at all subsequent scheduled clinic visits till Day 30 (EOS/ET) visit, standardized facial photographs will be taken per instructions in the study manual(s).

The facial photograph assessments will be conducted by a central facility. Results from the assessments will be used for reference purpose only and not be used to influence efficacy endpoint assessment at the site.

### **7.1.1.20 Facial Wrinkle Scale – Subject Assessment**

At the Screening Visit, Baseline (prior to dosing) Visit, and at all subsequent scheduled clinic visits till Day 30 (EOS/ET) visit, FWS at maximum frown and at rest will be assessed by the subject. Subjects will be provided the Photonumeric Guide prior to self-assessment to assist and standardize grading of GL severity. The FWS is a four-point scale that indicates severity of GL as follows: 0 = none, 1 = mild, 2 = moderate, or 3 = severe (see [Appendix 2](#) for sample FWS assessment sheet).

### **7.1.1.21 Facial Wrinkle Scale – Investigator Assessment**

At the Screening Visit, Baseline (prior to dosing) Visit, and at all subsequent scheduled clinic visits till Day 30 (EOS/ET) visit, FWS at maximum frown and at rest will be assessed by the Investigator. Investigator will be provided the Photonumeric Guide prior to assessment to assist and standardize grading of GL severity. The FWS is a four-point scale that indicates severity of GL as follows: 0 = none, 1 = mild, 2 = moderate, or 3 = severe (see [Appendix 2](#) for sample FWS assessment sheet).

## **7.2 Laboratory Procedures/Evaluations**

### **7.2.1 Clinical Laboratory Evaluations**

See [Sections 7.1.1.12](#), [7.1.1.13](#), [7.1.1.14](#), [7.1.1.15](#), [7.1.1.16](#), and [7.1.1.17](#).

### **7.2.2 Specimen Preparation, Handling, and Storage**

See Laboratory Manual for instructions of specimen preparation, handling, and storage.

### **7.2.3 Specimen Shipment**

See Laboratory Manual for instruction of specimen shipment.

### **7.2.4 Volume of Blood Collected**

The estimated total blood volume collected throughout the study for clinical laboratory and immunogenicity tests is summarized in [Table 4](#) and is expected to be approximately 59.5 mL.

**Table 4 Total Blood Volume Collected for Each Subject**

Test	Blood Sample Volume	Number of Tests	Total Volume
Hematology 	4 mL	3	12 mL
Serum chemistry  , Lipids, Serum pregnancy test 	8.5 mL	3	25.5 mL
HIV 1/O/2	5 mL	1	5 mL
HBsAG and HCV Ab	5 mL	1	5 mL
Serum samples for immunogenicity	4 mL	3	12 mL
TOTAL			59.5 mL

 Additional blood may be collected for safety laboratory tests, if clinically indicated

 Female of child bearing potential only

## 7.3 Study Schedule

### 7.3.1 Screening Visit (Days -30 to -1)

Screening (Visit 1, Days -30 to -1, inclusive) will include the procedures and evaluations set forth in [Section 7.3.7](#).

### 7.3.2 Baseline Visit (Day 0)

Baseline measurements and confirmation of subject eligibility will take place on Day 0. Procedures and evaluations prior to and after dose administration are set forth in [Section 7.3.7](#).

### 7.3.3 Follow-Up Visits (Days 1, 2, 7, AND 14)

Follow-up visits will take place on Days 1 ( $\pm 2$  hours), 2 ( $\pm 4$  hours), 7 ( $\pm 12$  hours), and 14 ( $\pm 1$  day). All procedures in each visit will be performed within the specified window. Procedures and evaluations for each follow-up visit are set forth in [Section 7.3.7](#).

### 7.3.4 End of Study (Day 30) / Early Termination Visit

Subject is considered to have completed the study after procedures and evaluations of Day 30 ( $\pm 2$  days) are performed. All procedures will be performed within the specified window. End of study (EOS) visit will include procedures and evaluations set forth in [Section 7.3.7](#).

In the event of early termination (ET), every attempt should be made to have subject return to the site to complete procedures and evaluations set forth in [Section 7.3.7](#).

[figure not shown]
### 7.3.5 Final Follow-Up Visit

The final follow-up visit on Day 42 ( $\pm 2$  days) will include the procedures and evaluations set forth in [Section 7.3.7](#). All procedures will be performed within the specified window.

### **7.3.6 Unscheduled Visit**

Unscheduled Visit, at the discretion of the Investigator, may occur and appropriate procedures and evaluations will be conducted and documented in the eCRF.

### 7.3.7 Schedule of Events Table

## 7.4 Concomitant Medications and Treatments

Throughout the study, the following concomitant medications and treatments are allowed and will be recorded.

- Regular moisturizer or sunblock creams or lotions.
- Medications used for controlled systemic disease or other medical conditions.
- Vitamins and herbal medicines.
- Acetaminophen for symptomatic relief of pain on an as needed basis, as prescribed by the Investigator.

The Investigator must notify the Sponsor if participants take other concomitant medications during the study. The decision to allow the subject to be enrolled into the study or take medications during the study will be made jointly by the Sponsor and Investigator, based on their opinion that the use of the medication is unlikely to compromise the safety of the subject or the interpretation of the study data.

## 7.5 Prohibited Medications, Treatments, and Procedures

During the study, subjects may not use the following medications, or have following treatments/procedures performed until after the EOS Visit.

- Any topical retinoid therapy or topical hormone cream applied to the face unless they have been on a consistent dose regimen and maintained the same regimen for at least 6 months before enrollment.
- Any oral retinoid drugs within 12 months of enrollment.
- Any drugs used for skin conditions within 3 months of enrollment.
- Any non-ablative resurfacing laser or light treatment, microdermabrasion, superficial peels within 3 months of enrollment.
- Any facial cosmetic procedure with medium depth to deep facial chemical peels (e.g., trichloroacetic acid [TCA] and phenol), or mid facial or periorbital laser skin resurfacing within 3 months of enrollment.
- Any mid-facial or periorbital treatment with non-permanent soft tissue fillers within 12 months of enrollment.
- Any history of botulinum neurotoxin treatment of any serotype.

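### The treatment ban in Section 7.5 ends at the Day 30 visit, leaving 8 to 16 days of safety follow-up with no explicit ban on other botulinum toxin or the listed facial procedures

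*Combined protocol and SAP*

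**What the plan says.** Section 7.5 opens its list with "During the study, subjects may not use the following medications, or have following treatments/procedures performed until after the EOS Visit". The list holds retinoids, skin drugs, laser and light treatments, peels, fillers and, as its last bullet, "Any history of botulinum neurotoxin treatment of any serotype".

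Section 7.3.4 places the end-of-study visit at Day 30 (± 2 days) and treats it as completion: "Subject is considered to have completed the study after procedures and evaluations of Day 30". Safety observation goes on after that. Section 7.3.5 adds "The final follow-up visit on Day 42" (also ± 2 days). Section 7.1.1.5 has adverse events recorded "until completion of the study until the final follow-up visit (Day 42"). Section 7.1.1.8 says "At Days 1, 2, 7, 14, 30 (EOS/ET), and 42 Visits, mini physical examination that is symptom-oriented will be performed" and attaches the focused neurological examination for spread of toxin to the same visits. Section 4.2.1 names that examination as a safety endpoint.

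Other provisions bear on the interval:

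- **Section 7.4** gives a short list of medications and treatments allowed throughout the study. Neither toxin nor any facial procedure is on it. For anything else, "The Investigator must notify the Sponsor if participants take other concomitant medications during the study", and the decision "will be made jointly by the Sponsor and Investigator".
- **Exclusion 5** (Section 5.2) keeps out anyone expected at entry to need another toxin during the study.
- **Section 5.4.1** permits, without requiring, termination of a subject who newly meets an exclusion criterion.
- **Section 7.1.1.9** has medications assessed at every visit.
- **Section 7.6** runs the ban on blood and plasma donation expressly to Day 42.

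**The concern.** The ban lifts while the study is still looking for the effects the ban would keep out. Table 1 lists drooping eyelid, blurred vision and muscular weakness among the likely symptoms of spread of botulinum toxin. If a subject received another toxin after Day 30, the Day 42 examination and late adverse event recording could pick up its effects.

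The event would then enter the all-event table (Section 10.4.4.5) and the neurological examination summary (Section 10.4.4.9) for that subject's dose group. Under Section 8.2.2 the attribution could go wrong either way. A possibly related event counts as related even when other factors may have contributed. A true late effect of EB-001 could be set aside because a clearly more likely explanation is present. In a first-in-human study with five active subjects per dose, preventing the ambiguity is better than adjudicating it.

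The toxin bullet has a separate drafting weakness. It describes past treatment, which is how an entry criterion is worded, so any rule on conduct after dosing rests on the lead-in sentence alone.

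**Working it through.** **Inputs**

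- End of the ban: after the end-of-study visit (Section 7.5), which is Day 30 ± 2, so Days 28 to 32 (Section 7.3.4).
- End of safety follow-up: Day 42 ± 2, so Days 40 to 44 (Section 7.3.5).
- Post-dose neurological examinations: Days 1, 2, 7, 14, 30 and 42 (Section 7.1.1.8).
- Last wrinkle rating: Day 30 (Sections 7.1.1.20 and 7.1.1.21).

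**The plan's own durations**

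- Dosing to follow-up: 42 / 7 = 6.0 weeks, matching the stated approximate 6 weeks.
- Earliest screening to follow-up: (30 + 42) / 7 = 10.3 weeks, matching the stated approximate 10 weeks.

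Day 42 is therefore the intended end of each subject's participation.

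**Length of the interval**

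| Case | Final follow-up − end-of-study visit | Days |
|---|---|---|
| Shortest | 40 − 32 | 8 |
| Nominal | 42 − 30 | 12 |
| Longest | 44 − 28 | 16 |

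This applies to subjects who attend both visits within window. For early terminations the interval is not defined. One of the six post-dose neurological examinations, at Day 42, comes after the ban has lifted. With the end point moved to the final follow-up visit, the interval is 0 days. No sample size or detection probability changes.

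**Does another provision close the interval?**

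- Section 7.4 comes closest, but it works by permission rather than prohibition. Its allowed list mentions treatments, while its notification and joint-decision rule speaks of medications only. It also depends on when the study ends for a subject: Section 7.3.4 points to Day 30, Section 7.1.1.5 links completion to Day 42, and Section 6.1.9 runs the whole study to the last subject's last visit.
- Exclusion 5 acts at entry.
- Section 5.4.1 is discretionary and acts after exposure.
- Section 7.1.1.9 records medications and forbids nothing.

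None is an explicit ban for the interval. Section 7.6 shows that the plan states a Day 42 limit where it wants one.

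**The case against.** The strongest reply is that the existing cover is substantial. Section 7.4's allowed list omits toxin and facial procedures. A toxin is a medication, so its use would need the Sponsor and Investigator to agree that it should neither harm the subject nor cloud the data. Subjects have never had toxin (exclusion 4) and expect no need for it (exclusion 5). This stands as partial cover. A reader might infer that toxin and procedures are uncontrolled after Day 30, and the documents do not support that. They support only the absence of an explicit ban.

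Ending the list at Day 30 is also coherent for most of its items, which concern skin appearance, because wrinkle ratings and photographs stop then. That is accepted for retinoids and skin drugs. It does not answer for toxin, and it answers only in part for procedures. Table 1 supports the mechanism for toxin. No passage says that a laser, peel or filler causes ptosis or weakness, so the case for procedures is weaker.

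The lead-in can be read so that the visit limit attaches to procedures only, leaving medications barred during the study. That is the less natural reading, and it returns to the unsettled question of when the study ends. It can also be said that if the toxin bullet is no conduct rule, the toxin gap is not 8 to 16 days. The figure here assumes that the lead-in makes it a rule.

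A reader might also quote one event as 1/5 = 20 percentage points in a dose group. That is true of any single event. The documents give no rate of such treatment, so it does not measure the harm.

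**Conclusion.** The point holds as a minor one and a cheap improvement. Between the Day 30 and Day 42 visits, 8 to 16 days (nominally 12) of planned safety observation have no explicit ban on another botulinum toxin or the facial procedures named in Section 7.5.

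A reader might infer that efficacy or dose-escalation results are compromised. The documents do not support that. Wrinkle ratings end at Day 30. The intolerable-dose rule in Section 10.4.4.4 needs two or more EB-001 subjects in a cohort with toxicities considered related. Dated event listings with relatedness (Section 10.4.4.5) would help a reader recognise a confounded event. What is at stake is clean attribution of late adverse events and of the Day 42 examination, mainly for toxin.

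The conclusion assumes that the lead-in's end point governs the whole list and that both visits occur within window. The schedule of events table and much of Section 4.1.1 are not visible, and Section 10.1 leaves the formal analysis plan to a later document. Nothing in the visible text contradicts the conclusion.

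**What to change.** In Section 7.5:

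- Replace the toxin bullet with a conduct rule: *any botulinum toxin other than study treatment*.
- Extend the ban on toxin, and on the laser, peel and filler procedures already named there, to the Day 42 final follow-up visit, except for medically necessary care. A ban on every facial procedure would go beyond the present list and is not needed.
- Let the retinoid and skin-drug limits end at Day 30 as now.
- Record any such treatment or procedure with its date, so that later adverse events can be identified in the listings.

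The cost is a short edit to one section, a dated procedure entry if the eCRF lacks one, and about 12 more restricted days per subject (8 to 16 with visit windows). No visit, assessment or sample size changes.
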